A significant disability is one that causes substantial disruption to the person's normal life and activity.

The investigator or designee must complete the SAE reporting (SAE100). Then relative to the event, a Revision/Removal Form (RR 100), and/or the Withdrawal Form (WD100) form should be completed. See the Implant Retrieval and Analysis of Removed Implants section below for instructions on how to handle investigational devices that are removed from study subjects.

DISCONTINUATIONS AND REVISIONS (SUBJECT WITHDRAWAL)

It is recognized that the subject's participation in this trial is entirely voluntary, and that she/he may refuse to participate and may withdraw from participation at any time without jeopardy to any future medical care. Device Revision or Removal is also considered a withdrawal event when all components are removed, or if only the humeral stem is removed. No additional study follow-up is necessary. In the event that a patient receives a partial revision (not all components/humeral stem), a revision/removal form should be completed, but the patient should still be followed per protocol. Do not complete a withdrawal form for these patients. *Enrollment for this study is defined as receipt of either a control or an investigational device.*

Therefore:

- Subjects withdrawn from the study after receipt of either the control or investigational device will NOT be replaced.
- Randomized patients who do not ultimately receive the control or investigational device:
 - 1. *WILL* be replaced, but
 - 2. Randomization assignment will not be re-used
- *All* subject withdrawals must be documented on the Withdrawal Form (WD100).

- Includes randomized patients who do not ultimately receive the control or investigational device configurations.
- If withdrawal is due to device removal or revision, the SAE 100 form must be completed. The Revision/Removal form (RR 100) should be completed in all cases including device removal details, if known.

Copies of all Case Report Forms are included in Exhibit 4.

CONTROL OF INVESTIGATIONAL DEVICE

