Absence of Revision/Removal/UADE

¹ Dmitrienko, Alex, et al. *Analysis of Clinical Trials Using SAS.* SAS Publishing, 2005, pp75-76.

The proportion of successful outcomes (i.e., patients not requiring a revision/removal of any device component or receiving a UADE during the course of the study) in the Investigational group is non-inferior to the proportion of successful outcomes in the Control group using a 10% margin of non-inferiority. The test is based on the lower bound of a one-sided 95% confidence interval for the difference, Investigational minus Control, in proportions of success at 22+ months. A conclusion of non-inferiority is supported if the lower bound of the confidence interval is at least -0.10.

American Shoulder and Elbow Surgeons Score

The mean American Shoulder and Elbow Surgeons (ASES) Score for the Investigational group is non-inferior to the mean ASES score for the Control group using a 9.5-point margin of noninferiority. This margin is based on an approximation that is sometimes used for the MCID based on the observation that for many patient-reported outcome measures, the MCID is about half the SD of change². This method is mentioned as well in an article by Singh et. al, where a half-standard deviation is mentioned as a generally accepted clinically significant benchmark³. Information about plausible values of the standard deviations ASES scores are available in an article by Angst, et. al.⁴ This article gives a standard deviation of postoperative ASES score for 142 subjects of 19.0 points, giving a half-standard-deviation of 9.5 points.

This test will be based on the lower bound of a one-sided 95% confidence interval for the difference, Investigational minus Control, in means at 22+ months. A conclusion of non-inferiority is supported if the lower bound of the confidence interval is at least -9.5 points.

RANDOMIZATION DETAILS

Study: Comprehensive® nano

² Murray et al. "The use of the Oxford hip and knee scores." *JBJS(Br)*. 2007; 89-B 1010-14.

³ Singh, Jasvinder et. al. "Challenges with health-related quality of life assessment in arthroplasty patients: Problems and solutions". *J Bone Joint Surg* 2010; 18:72-82.

⁴ Angst et. al. "Responsiveness in Shoulder Arthroplasty Outcome Instruments." Arthritis & Rheumatism (Arthritis Care & Research) Vol. 59, No. 3, March 15, 2008, pp 391–398

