Non-inferiority sample size calculations were implemented in nQuery Advisor 7.0 software using a 1:1 ratio of Investigational to Control subjects. This software uses methodology of the two-group t-test of equivalence in means as described in a text by Dixon and Massey⁸ as well as in a text by O'Brien and Muller.⁹

The sample size needed to obtain 90% power for testing the hypothesis above was calculated as follows:

Definitions:

- μ_l : Mean ASES score for the Investigational (Stemless Shoulder) treatment group.
- μ_{C} : Mean ASES score for the Control (Total Shoulder) treatment group.
- δ: Non-inferiority margin. Lower 95% confidence bound for difference in mean ASES scores at 22+ months (Investigational Control) must be greater than –δ.

For a specified constant, $0 < \delta < 1$, the hypotheses of non-inferiority are:

 $H_0: \mu_I - \mu_C \leq -\delta \ vs. \ H_1: \mu_I - \mu_C > -\delta.$

Information about plausible values of the standard deviations ASES scores are available in an article by Angst, et. al.¹³ This article gives a standard deviation of postoperative ASES score for 142 subjects of 19 points.

Assumptions:

$\alpha = 0.05$	Probability of Type I error
$\beta = 0.10$	Probability of Type II error: power = $1 - \beta$

¹³ Angst et. al. "Responsiveness in Shoulder Arthroplasty Outcome Instruments." Arthritis & Rheumatism (Arthritis Care & Research) Vol. 59, No. 3, March 15, 2008, pp 391–398.

$s_{C} = s_{I} = 19$	Estimated standard deviation of ASES scores for Control and
	Investigational groups
δ = 9.5	Non-inferiority Margin

Resulting sample sizes (number of shoulders), not adjusted for attrition, are 70 Investigational vs. 70 Control (5% type I error rate, 90% power). The sample size was increased by 15% to allow for possible attrition. This gives a sample size of 166 total subjects (83 Investigational and 83 Control).

STUDY POPULATIONS

ALL ENROLLED POPULATION

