Subjects who have been randomized to the Investigational or Control group in this study comprise the All Enrolled population. The co-primary endpoints will be analyzed for the All Enrolled population and the results will be compared to the primary analyses performed on the Analysis population to determine whether the results of this analysis are consistent for both populations. For patients in the All Enrolled Population who are missing data necessary for the determination of any of the co-primary endpoints at 22+ months, data will be imputed as described below in the section "Sensitivity Analyses."

ANALYSIS POPULATION

Subjects who have been randomized to the Investigational or Control group in this study and who have complete data for a primary endpoint collected per the protocol at 22+ months or who have had a revision or removal at or before 26 Months will be included in the Analysis Population. This is the population that will be used in the primary study analysis and determination of study success. Those subjects who are missing their primary endpoint at 22+ months will be included as part of the All Enrolled population described above. Subjects with protocol deviations will be analyzed on an individual basis to determine if they will be included in the Analysis Population.

MISSING DATA AND SENSITIVITY ANALYSES

Data will be considered "missing" for a given primary endpoint if this endpoint cannot be calculated or is not available for a subject in the All Enrolled population. If the subject has had a

device failure at any point on or prior to their 22+ month outcome, they will *not* be considered as missing data for the Absence of Revision/Removal/UADE endpoint, as this endpoint is cumulative. A subject who has had a revision or removal prior to two years will be considered a radiographic failure at the 22+ month time point for purposes of the primary analysis. When possible (i.e. the subject is seen by a study investigator in a non-emergency situation and collection of the data will not cause undue burden), ASES scores will be collected for these cases before the revision is performed in order to prevent these patients from missing knee scores in the primary efficacy analyses.

Sensitivity analyses will examine the sensitivity of the results to missing values of the primary outcomes using the following analyses:

Outcome Type	Analysis Description	
Binary	Tipping Point Analysis: Missing observations are replaced with	

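### A shoulder withdrawn after full or humeral-stem removal has no fallback ASES value in the primary analysis, which favours the arm revised more often

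*Combined protocol and SAP*

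**What the plan says.** Under Discontinuations and Revisions (Subject Withdrawal), removal of all components or of the humeral stem alone is a withdrawal event, and "No additional study follow-up is necessary". A partial revision that leaves the humeral stem in place stays in follow-up.

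Under Study Populations, a shoulder revised or removed by 26 months is in the Analysis Population, which decides study success. Under Missing Data and Sensitivity Analyses:

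- The revision endpoint is cumulative, so a revised shoulder is never missing on it.
- A revision before two years counts as a radiographic failure.
- For ASES the instruction is that "ASES scores will be collected for these cases before the revision is performed", with a condition in front: "When possible (i.e. the subject is seen by a study investigator in a non-emergency situation" and collection is not unduly burdensome. The stated aim is to avoid missing scores in the primary efficacy analyses.

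No value is given for a shoulder that does not meet the condition.

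Under Efficacy Evaluations, the ASES bound is built from the two observed arm means, standard deviations and counts. Missing ASES is imputed (100, 0, last observation carried forward, multiple imputation) only in the sensitivity analyses. A tipping-point analysis is listed for the binary endpoints only.

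**The concern.** One event is handled in two ways. A humeral-stem removal counts against the device on the revision endpoint and, before two years, on the radiographic endpoint. On ASES the same shoulder can disappear, because a mean of observed scores has nowhere to put it. Shoulders heading for removal can be expected to score below the rest, so omitting them raises the mean of the arm that loses more of them. The risk section itself says that the stemless design may carry a higher risk of loosening or migration, so unequal revision rates cannot be ruled out. At stake is the error rate of one of three co-primary tests.

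**Working it through.** **Inputs from the plan.** The ASES test is run "using a 9.5-point margin of noninferiority". The SD is 19, from a cited "standard deviation of postoperative ASES score for 142 subjects of 19.0 points". The criterion is the "lower bound of a one-sided 95% confidence interval for the difference, Investigational minus Control, in means at 22+ months". Power is 90% and allocation 1:1. The revision rate used for planning is 2% (1 of 49). The revision endpoint has a 10-point margin and a planned success rate of 95%, which leaves 3% for failures other than revision.

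**The plan's own figure.** n per arm = 2 × (1.645 + 1.282)² × (19/9.5)² = 68.5, so 69 by the normal approximation. The noncentral t gives power 0.8993 at 69 and 0.903 at 70, hence the stated 70. Then 70/0.85 = 82.4, so 83 per arm and 166 in total, as stated.

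**Assumptions the documents do not supply.** Unrevised control mean 80; failed shoulders at 40 (the entry ceiling) or, more harshly, at 0; nano revision 5%, 8% or 10%. I use 112 shoulders per arm, the radiographic sample size before attrition.

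**Size of the shift.** Let r be the proportion revised without a score, m the mean of unrevised shoulders and v the value of a failed shoulder. Omitting the failures moves the difference in favour of nano by

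shift = r_I(m_I − v) − r_C(m_C − v).

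With both unrevised means at 80 and v = 40, this is (0.05 − 0.02) × 40 = 1.2 points, or (0.08 − 0.02) × 40 = 2.4 points.

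**False-pass rate of the ASES test.** Fix the true all-shoulder difference at −9.5. The all-shoulder control mean is 0.98 × 80 + 0.02 × 40 = 79.2, so the nano mean is 69.7.

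- Nano revision 5%: m_I = (69.7 − 0.05 × 40)/0.95 = 71.26. The analysed difference is −8.74, a shift of 0.76. SE = 19 × √(1/106.4 + 1/109.8) = 2.58. Pass rate = 1 − Φ(1.645 − 0.76/2.58) ≈ 9%.
- Nano revision 8%: m_I = (69.7 − 0.08 × 40)/0.92 = 72.28. The analysed difference is −7.72, a shift of 1.78. SE = 19 × √(1/103.0 + 1/109.8) = 2.61. Pass rate = 1 − Φ(1.645 − 1.78/2.61) ≈ 17%.
- Equal 2% in both arms: the same steps give a shift of −0.19 and a pass rate of about 4%, so there is no inflation.

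**Simulation with the plan's bounds**, all at a true difference of −9.5, with 3% other failures per arm on the revision endpoint:

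| Failed value | Nano revision | ASES passes, no scores captured | ASES passes, failures included | Revision endpoint passes | Both pass, no scores captured | Both pass, failures included |
|---|---|---|---|---|---|---|
| 40 | 5% | 9% | 5% | 71% | 6% | 4% |
| 40 | 8% | 17% | 5% | 34% | 6% | 3% |
| 40 | 10% | 25% | 5% | 17% | 4% | 2% |
| 0 | 5% | 19–20% | 5% | 71% | 14% | 5% |
| 0 | 8% | 52% | 5% | 34% | 18% | 4% |
| 0 | 10% | 75% | 6% | 17% | 13% | 3% |

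If half of the pre-revision scores are captured and failures sit at 40, the ASES pass rate falls to about 7% (5% nano revision) and 8–10% (8%).

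**Limit set by the revision endpoint.** At 112 to 132 per arm and 2–5% control failures, the largest observed nano excess that still passes is about 3.6 to 5.4 percentage points. If every excess failure were an unscored revision, the ASES shift would be 1.4–2.1 points with a 40-point gap, or 2.9–4.3 with an 80-point gap.

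**The case against.** The strongest reply is that excess revisions cannot slip past the trial. Success needs all three co-primaries, and revision counts as failure on one of the others, or on both if it occurs before two years. That stands, and it disposes of a tempting stronger reading: that the ASES rule conceals poor nano outcomes from the overall decision. A reader might take 12% against 2% revision, get a shift of 0.10 × 40 = 4 points (42% of the margin), and call the trial unsafe. But that revision difference lies on the 10-point margin of the revision endpoint, which passes only about 7% of the time there.

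Second, collection before revision is planned, with stated exceptions, and is meant to feed the primary analysis. The figures for no capture are therefore a ceiling. A reader might also infer that the uncollected cases are the worst ones; the documents do not say so.

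Third, partial revisions that keep the humeral stem continue in follow-up and can give a 22+ month score, so the gap does not cover every revised shoulder.

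Fourth, missing ASES is already stress-tested, including at 0, which is harsher than a preoperative value. However, those analyses do not determine success, and the fixed-value ones treat every missing score alike, whatever the cause. Carrying the last observation forward may import a good score from before the failure, and no ASES tipping point is listed.

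**Conclusion.** The gap is real and its direction is known: the primary ASES analysis has no value for a withdrawn revised shoulder without a pre-revision score, and dropping it favours the arm revised more often. With failed shoulders at 40 and control revision at 2%, the ASES false-pass rate rises from 5% to about 9–17% at 5–8% nano revision with no scores captured, and to about 7–10% with half captured. The chance of passing ASES and the revision endpoint together stays near 6%. It reaches about 14–18% only if failed shoulders score 0 and none is captured. At equal revision rates there is no inflation.

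The unrevised mean, failure values, nano revision rates and capture rates are assumptions. This is worth correcting because each co-primary test should be valid by itself and the correction is cheap. It is not a defect that would by itself let a clearly worse device through.

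**What to change.** Add one paragraph to the SAP. Every shoulder withdrawn for revision or removal by 26 months enters the primary ASES analysis with the score from its pre-revision assessment; if none was collected, it enters with its preoperative ASES. That score is collected for every shoulder, reviewed by the sponsor before enrolment, and cannot exceed 40 in an eligible patient. Both sources are objective and need no judgement about when failure began. State also which score applies if a 22+ month ASES was already recorded before a revision within that window.

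Report the analysis with these shoulders omitted as sensitivity, and add a tipping-point analysis for ASES in which the imputed value varies separately by arm.

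Reconcile three points of text:

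- The list of discontinuation reasons under Secondary Endpoints names revision/removal without exception, whereas the Discontinuations section keeps partial revisions in follow-up. How many shoulders this point affects depends on that.
- The radiographic rule uses two years as its limit, while the Analysis Population uses 26 months.
- The sentence on pre-revision collection refers to knee scores in a shoulder trial.

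The cost is that the ASES mean becomes partly failure-inclusive and slightly lower. No visits, data items or added sample size are needed.

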Complete eligibility checklist	x					
Complete Patient History Form: HX100	x					
Complete ASES Assessments: ASES100	x		х	x	х	х
Complete SANE Assessment: SANE100			x	x	x	х
Complete Constant Score Form: CST100	х		X**	x	х	х
Randomize Patient		х				
Record Operative Details: OP100		х				
Collect Radiographic Images (AP Int., AP Ext, and Axillary Views)			x	x	x	x
Protocol Deviation Form: PD100	As needed	As needed	As needed	As needed	As needed	As needed
Complete Adverse Event Form: AE100 and/or Serious Adverse Event SAE100	As needed	As needed	As needed	As needed	As needed	As needed
Complete patient Withdrawal Form: WD 100		As needed	As needed	As needed	As needed	As needed
Complete Device Revision/Removal: RR100			As needed	As needed	As needed	As needed

Each follow-up visit time point will be determined based on the date of surgery.

** At the 6 week interval, in order to protect the subscapularis repair, the strength and ROM sections are not to be completed by sites.

*** Annual follow up will continue until study closure or until the last enrolled patient reaches their 2 year follow up window.

BILATERAL PATIENTS

A patient undergoing staged bilateral surgery must sign a consent form **for each study procedure**. Each study shoulder will be randomized separately. Bilateral patients will be required to wait at least 9 months between procedures for the purposes of the study.

Patients with staged bilateral study implants will require two ASES, Constant Score, and SANE assessment forms to allow individual assessment of each operative side over the course of the study. Patients must be instructed to assess each shoulder individually, i.e., only record right-shoulder pain levels on the CRF for their right shoulder and only report left shoulder pain on the CRF for the left shoulder.

SCHEDULE OF FOLLOW-UP ASSESSMENTS

Post-operative clinical and radiographic evaluations will be performed according to the following schedule, with the associated visit windows:

- 6 weeks (± 2 weeks)
- 3 months (± 2 weeks)
- 1 year (± 2 months)
- 2 years (± 2 months)
- Annually thereafter* (± 2 months)
- * Until all patients reach the 2-year visit window or the study is closed

ASSESSMENT PARAMETERS AND METHODS

Pre-Operative Visit - Medical History, Demographic Data and Patient Eligibility

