Demographic information will be collected so that valid comparisons can be made between the control and investigational groups. Detailed medical history will be obtained in accordance with the physician's clinic practice.

Eligibility will be determined by the collection of medical history, intraoperative criteria, and any other tests deemed relevant by the investigator and/or his or her institutional review board. Any tests that are to be conducted that are NOT part of the investigator's

normal clinical practice but are specific to this clinical study must be done after the patient has reviewed and signed the approved Informed Consent Form.

Clinical and Operative Assessments

An Operative Record Case Report Form will be completed to record details of group assignment, components implanted, and any operative complications. Post-operative clinical data will be collected utilizing recognized, validated scoring systems (ASES, Constant, and SANE scores). Radiographic images and Adverse Event data will be collected and submitted to the sponsor for independent assessment.

Radiographic Assessments

Three views are required for each study shoulder at each postoperative time point; glenohumeral Anterior-Posterior (AP) in internal and external rotation and axillary radiographs. All radiographic images will be assessed for radiolucencies, osteolysis, and component movement (subsidence, migration) by a centralized independent radiographic reviewer, utilizing the 6-week visit as the baseline radiograph.

PROTOCOL DEVIATION MANAGEMENT AND REPORTING

Any deviation from the FDA and IRB-approved study protocol or any other applicable regulatory requirements is considered a protocol deviation and must be reported to the sponsor using the Protocol Deviation Case Report Form (PD-100) as soon as they are known by the investigator.. Any Protocol Deviation will be assessed for effect on patient safety or the validity of the data. Please refer to the Statistical Analysis Plan section for details on how protocol deviations will be analyzed. According to 21 CFR Part 812.150(a)(4), an investigator shall notify the sponsor and the reviewing IRB of any deviation from the investigational plan to protect the life or physical well-being of a subject in an emergency. Such notice shall be given as soon as possible, but in no event later than 5 working days after the emergency occurred.

ADVERSE EVENT MANAGEMENT AND REPORTING

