The three co-primary endpoints for this study are:

- a. ASES score at 22+ Months
- b. No unanticipated device-related adverse event, and no fracture, perforation of the bone or joint dislocation, and no fracture, perforation or dissociation of the device, and no revision or removal of any component, and
- c. Radiographic Success, as defined by:
 - a. Subsidence of the humeral component < 5 mm, and
 - b. Migration of the humeral component < 5mm, and
 - c. No progressive lucency around the humeral component >2mm in two or more contiguous zones
 - d. Migration of the glenoid component <5 mm, and
 - e. No progressive lucency >2mm around the entire glenoid component

SECONDARY ENDPOINTS

The data collected will also be analyzed for the following secondary endpoints:

- 1. American Shoulder and Elbow Surgeon's Score (ASES) at all time points
- 2. Single Assessment Numeric Evaluation (SANE) Score at all time points
- 3. Constant Score at all time points, except 6 weeks (adjusted for age and gender)
- 4. Radiographic assessment of radiolucencies and subsidence
- 5. Overall adverse events including removal/revision and other serious adverse events

The safety of the system will be monitored by recording adverse events including serious adverse events not considered UADEs throughout the follow-up period. Types of events to be collected include but are not limited to:

- Device removal or revisions
- Unanticipated adverse device events
- Systemic adverse events
- Local adverse events
- Reoperations and Other Interventions

Study participants will only be considered discontinued/withdrawn for the following reasons:

- Death
- Withdrawal of consent (written)
- Revision/Removal

Information from any patient who fails to return for multiple, consecutive, scheduled follow-up visits for any reason other than the criteria listed above will be identified as Missing Data.

ANTICIPATED CHANGES

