(Radiographic Success,	values until the lower limit of the 95% Confidence interval for the	
Absence of	difference in proportions is equal to the non-inferiority margin	
Revision/Removal))	(the tipping point). Graph will show which imputations of	
Kevision/Kemovaljj	success/failure for the missing values in the investigational and	
	control groups lead to a conclusion of inferiority, and which lead	
	to a conclusion of non-inferiority. Missing Values as Success: Imputation of missing values as	
	"success"	
	Missing Values as Failures: Imputation of missing values as	
	"failure"	
	lanure	
	Last Observation Carried Forward: Missing observations in	
	either group are imputed by taking the most recent outcome prior	
	to 24 months and using it in place of the missing 24-month	
	outcome.	
	2 Year In-Window Analysis : Only data collected within the 2-	
	year per-protocol visit window (22-26 months) are included in	
	this analysis.	
	Multiple Imputation: This method replaces each missing value	
	with a set of plausible values that represent the variability around	
	the choice of which value to impute.	
Continuous	Replace with Maximum: Imputation of missing ASES as "100"	
(ASES Score)		
	Replace with Minimum: Imputation of missing ASES as "0"	
	Last Observation Carried Forward: Missing observations in	
	either group are imputed by taking the most recent outcome prior	
	to 24 months and using it in place of the missing 24-month	
	outcome.	
	2 Year In-Window Analysis : Only data collected within the 2-	
	year per-protocol visit window (22-26 months) are included in	

this analysis.
Multiple Imputation: This method replaces each missing value
with a set of plausible values that represent the variability around
the choice of which value to impute.

In addition, in the event that one or more subjects receive the opposite treatment than the one they were randomized to receive, a sensitivity analysis will be done on patients "as randomized" to make sure it is consistent with the primary analysis ("as treated"). However, because randomization will be performed intra-operatively and the patient must be able to receive either treatment in order to be randomized, this situation is not expected to occur. Other sensitivity analyses will be conducted as needed (i.e. if the effect of missing data on a particular primary outcome is still unclear).

TESTS FOR INTERACTION

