BASELINE CHARACTERISTICS

Subjects in the Investigational and Control study groups will be compared regarding a list of baseline items, including preoperative ASES and Constant Scores, demographics (age, gender, and primary diagnosis), medical history, and comorbidities.

EFFICACY EVALUATIONS

Primary Endpoint

The confidence intervals used in the analysis of the binary primary endpoints (Radiographic Success and Absence of Revision/Removal/UADE) will be 1-sided, 95% confidence intervals for the difference between proportions in two independent samples. They will be calculated using the Wald method as based on a normal approximation to the binomial, as follows:

$$(p_C - p_I) + z_\alpha \sqrt{SE_C^2 + SE_I^2}$$

Where

 p_{C} = proportion of success in the Control group, p_{I} = proportion of success in the Investigational group, α = 0.05, and

$$SE_C = \sqrt{\frac{p_C(1-p_C)}{n_C}}$$
 and $SE_I = \sqrt{\frac{p_I(1-p_I)}{n_I}}$

The confidence interval used in the analysis of the continuous primary endpoint (ASES Score) will be a 95% confidence interval for the difference between means in two independent samples. They will be calculated using the normal distribution, as follows:

$$(\overline{x}_C - \overline{x}_I) + z_\alpha \sqrt{\frac{s_C^2}{n_C} + \frac{s_I^2}{n_I}}$$

Where

 x_{C} = mean ASES score in the Control group,

 $\overline{x_{I}}$ = mean ASES score in the Investigational group,

 $s_{\scriptscriptstyle C}$ = standard deviation of the ASES scores for the Control group,

 s_{T} = standard deviation of the ASES scores for the Investigational group, and

 $\alpha = 0.05$

Secondary Endpoints

Secondary outcomes include the ASES score, SANE score, Constant score, and radiographic endpoints at 6 weeks, 6 months, 1 year, and 2 years separately. These outcomes will be compared for Investigational and Control groups at each time point.

Exploratory Analyses14

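### Last observation carried forward for Radiographic Success does not exclude the 6-week baseline film, so an unrevised shoulder with no later film is imputed as a success by construction

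*Combined protocol and SAP*

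**What the plan says.** **The imputation rule.** Missing Data and Sensitivity Analyses lists six analyses for the binary endpoints. Under last observation carried forward (LOCF), missing values in "either group are imputed by taking the most recent outcome prior" to 24 months. No minimum follow-up is set and no visit is excluded.

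**The radiographic baseline.** Under Radiographic Assessments, a central independent reader assesses lucency, osteolysis, subsidence and migration, "utilizing the 6-week visit as the baseline radiograph".

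**The endpoint.** Co-Primary Endpoints defines Radiographic Success by movement and progression. Two of its five conditions are "Subsidence of the humeral component < 5 mm, and" and "No progressive lucency around the humeral component >2mm in two or more contiguous zones". The other three are limits on humeral migration, glenoid migration and progressive glenoid lucency.

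**A 6-week reading exists.** The secondary endpoints under Efficacy Evaluations include "radiographic endpoints at 6 weeks, 6 months, 1 year, and 2 years separately".

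**Revised shoulders.** "A subject who has had a revision or removal prior to two years will be considered a radiographic failure" at the 22+ month time point in the primary analysis.

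**Where LOCF is used.** Study success is decided on the Analysis Population. The All Enrolled Population section sends missing co-primary data to the imputations in the sensitivity section and compares the results with the primary analysis for consistency.

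**The concern.** A sensitivity analysis for missing films should show whether the radiographic conclusion depends on what happened to the shoulders that were not filmed at two years. LOCF is usually read as the analysis that uses each patient's own data. For a shoulder with only the 6-week film there is no such information: the carried value compares the baseline with itself and cannot be a failure.

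This matters for this device in particular. The risk section names failed biologic fixation, with loosening or migration, as the risk that may be raised by the stemless design. A rule that scores zero observed migration time as success cannot see that risk in the shoulders concerned. If LOCF then agrees with the primary result, the agreement partly reflects the rule and not the data.

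**Working it through.** **Inputs from the plan.** Success rate 0.93 in both arms, margin 0.10, one-sided alpha 0.05, power 90%, 15% attrition allowance (Sample Size Calculation, Radiographic Success); unpooled Wald interval (Efficacy Evaluations, Primary Endpoint).

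**Step 1. Reproduce the plan's sample size.**

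n = (1.645 + 1.282)² × 2 × 0.93 × 0.07 / 0.10² = 111.5, so 112 per arm; 112 / 0.85 = 131.8, so 132 per arm. Both match. The allowance is 132 - 112 = 20 shoulders per arm.

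**Step 2. Value imputed to a baseline-only shoulder.** The 6-week film minus itself gives 0 mm of subsidence and migration, below 5 mm, and nothing can have progressed. All five conditions are met, so the imputed value is success.

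**Step 3. Effect on the bound.** Lower bound = (pI - pC) - 1.645 × √[pI(1 - pI)/nI + pC(1 - pC)/nC]. The plan writes this as an upper bound for Control minus Investigational, which is the mirror image. If k successes are added to n observed shoulders in each arm, the difference is multiplied by n/(n + k); here 112/132 = 0.848.

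The observed counts are assumed for illustration. The documents do not say how many shoulders would have only a 6-week film. Twenty per arm takes the whole allowance as such losses and is an upper illustration.

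| Case | Investigational | Control | Difference | Lower bound |
|---|---|---|---|---|
| Complete cases | 99/112 | 104/112 | -0.0446 | -0.1085 |
| 5 per arm carried from 6 weeks | 104/117 | 109/117 | -0.0427 | -0.1040 |
| 10 per arm carried | 109/122 | 114/122 | -0.0410 | -0.0999 |
| 20 per arm carried | 119/132 | 124/132 | -0.0379 | -0.0925 |
| 20 per arm imputed as failure | 99/132 | 104/132 | -0.0379 | -0.1231 |
| Unbalanced: 5 and 20 carried | 104/117 | 124/132 | -0.0505 | -0.109 |

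**Step 4. A case where the primary analysis passes.** With 104/112 in each arm, the complete-case bound is -0.0566 and LOCF with 20 carried per arm (124/132 each) gives -0.0483. Suppose 7 of the 20 lost investigational shoulders and 1 of the 20 lost control shoulders had in truth failed. The full data would be 117/132 against 123/132, with a bound of -0.1035. LOCF would still report -0.0483.

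**Step 5. Simulation at the null boundary.** True success 0.83 against 0.93, 132 per arm, a share of each arm lost at random after the 6-week film, 400,000 simulated trials per row:

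| Share lost (shoulders per arm) | LOCF declares non-inferiority | Complete cases |
|---|---|---|
| 0% (0) | 5.6% | 5.6% |
| 5% (7) | 7.3% | 5.8% |
| 10% (13) | 9.1% | 5.5% |
| 15% (20) | 11.8% | 5.5% |
| 20% (26) | 14.7% | 5.6% |

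The shift appears even though loss is random and equal between arms.

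**The case against.** **LOCF decides nothing, and better checks are planned.** This stands. Study success rests on the Analysis Population, where the 99/112 example already fails; a pass under LOCF could not rescue it. The tipping-point analysis maps the success and failure imputations in both arms, and the worst case is also planned ("Missing Values as Failures: Imputation of missing values as" failure); it gives -0.1231 in the example. Multiple imputation is planned too. The false reassurance is confined to one of six rows and to the All Enrolled comparison that draws on it.

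**A reader might infer that the rule always favours non-inferiority and can never reveal a problem.** The documents do not support that. With 5 investigational and 20 control baseline-only shoulders, the bound moves from -0.1085 to -0.109, away from non-inferiority. LOCF also carries any failure seen at 3 months or 1 year, and revised or removed shoulders count as failures.

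**The size depends on an extreme assumption.** This stands as well. A shoulder lost after 3 months carries a real post-baseline film, so 20 baseline-only losses per arm is a ceiling. The crossing of the margin is also fragile: 10 per arm only just passes and 5 per arm does not.

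**Perhaps a 6-week composite is not an outcome at all.** Progression cannot be judged from one film, so such a shoulder could be regarded as having no outcome to carry. That is a sensible reading, but the LOCF row does not state it, and radiographic endpoints are listed for analysis at 6 weeks. Exhibit 3, the radiographic protocol, is not in the text available for review, so a restriction there cannot be ruled out.

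**A reader might extend the point to ASES.** The text does not carry it that far. An early ASES score is a measured value, not a success by construction, and no bias of fixed direction follows. The Table 1 footnote about protecting the repair at 6 weeks belongs to the Constant Score row.

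**Conclusion.** The concern holds in a limited form. As written, the LOCF rule allows the 6-week baseline film to stand for the two-year radiographic outcome, and for an unrevised shoulder with no later film that value is a success whatever the implant did later. With similar losses in both arms and a worse investigational arm, the LOCF result moves toward non-inferiority: at most from -0.1085 to -0.0925 in the illustration, and from about 5.6% false declarations to between 7.3% and 14.7% at the null boundary for 5% to 20% baseline-only loss. These sizes assume losses between the 6-week and 3-month films that the documents neither give nor exclude; the true number is probably much smaller than 20 per arm. The primary decision is unaffected. The point merits correction because a stated rule yields a value with no information behind it and the repair is nearly free.

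**What to change.** Add to the LOCF row for Radiographic Success:

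- The 6-week baseline film is never carried forward.
- Only a post-baseline film may be carried, and any failure observed at 3 months or later is kept as a failure.
- Shoulders with only a baseline film stay missing in the LOCF analysis and are covered by the planned tipping-point, missing-as-failure and multiple-imputation analyses.

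Because the All Enrolled Population section says missing co-primary data will be imputed, it needs a short cross-reference to this exception. Reporting the number of baseline-only shoulders per arm beside the LOCF result would let a reader judge its weight.

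A stricter rule admitting only films from 1 year onward is not needed. It would turn a failure seen at 3 months in a shoulder later lost unrevised into missing data.

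Cost: one or two sentences and no new data. LOCF will cover slightly fewer shoulders and may look slightly less favourable.
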